4. EFFICACY, PHARMACOKINETICS, PHARMACODYNAMICS AND ANTI-DRUG ANTIBODIES ANALYSES

4.1 EFFICACY AND QOL

4.1.1 Available data

Efficacy will be assessed using MG-ADL. Quality of life will be measured using 15-item Quality of life scale for Myasthenia Gravis [revised version] (MG-QoL15r) and EuroQoL 5 Dimensions 5 Levels (EQ-5D-5L).

4.1.2 Endpoints and derivation rules

- 1) Actual values and change from baseline and CnB in MG-ADL total score will be analyzed descriptively and categorically.

Categories to be used for actual values in MG-ADL total score: 0, 1, 2, 3, 4, 5-7, 8-9, 10-12, 13-16, 17-20 and 21-24.

Of note, minimum symptom expression (MSE) is a MG-ADL total score of 0 or 1.

Categories to be used for changes from baseline and CnB in MG-ADL total score: >0, 0, -1, -2, -3, -4, -5, -6, -7, -8, -9, -10, <-10. Number of participants, percentages and cumulative percentages will be shown.

In addition to the planned timepoints, following timepoints will be shown for each cycle:

- Maximum drop from baseline and CnB in MG-ADL
- Minimum MG-ADL score: descriptively and categorically

Missing data will not be imputed.

Analysis will be done by AChR-Ab status (repeat for AChR-Ab seropositive participants, then for AChR-Ab seronegative participants), by type of visit (on-site visit vs by-phone visit), by region, and overall.

- 2) Actual values and change from baseline and CnB in MG-QoL15r total score.
- 3) Actual values and change from baseline and CnB in EQ-5D-5L VAS score.

4.1.3 Statistical analysis

Summary statistics will be provided in terms of absolute values and changes from baseline (overall) and CnB (for each cycle) for MG-ADL total scores on the overall safety population and by AChR-Ab status. Both tables will be repeated by average treatment duration per year. Additionally, summary statistics will be provided in terms of absolute values and change from baseline over time by average treatment duration per year.

The table on overall safety population by cycle will be repeated by type of visit and by region (see 3.3.2).

Absolute values and changes from baseline (overall) and CnB (for each cycle) in MG-ADL total scores will also be shown categorized, including the number of participants within each category, the percentage and the cumulative percentage. This

Statistical Analysis Plan

ARGX-113-2002

Final Analysis

Final 5.0 of 31Jan2025

will be done for the overall safety population and by AChR-Ab status. Both analyses on the actual values will be repeated by average treatment duration per year

Summary statistics will be provided in terms of absolute values and changes from baseline (overall) and CnB (for each cycle) for MG-QoL15r total score and EQ-5D-5L VAS score in the overall safety population and by AChR-Ab status.

See section 8 for a list of tables and listings.

4.2 MEDICAL RESOURCE UTILIZATION AND HEALTH ECONOMICS

4.2.1 *Available data*

4.2.2 *Presentation of results*

Statistical Analysis Plan

ARGX-113-2002

Final Analysis

Final 5.0 of 31Jan2025

4.3 PHARMACOKINETICS

4.3.1 Available data

Blood samples for determination of serum concentrations of efgartigimod will be collected at the time points indicated in the schedule of assessment (Section 9.4).

PK samples will be allocated to the analysis visit windows defined in section 2.2.4.

Time windows for PK samples are specified as follows:

- On TPnV1: prior to the injection;
- On visits for additional PK sampling (ie, PK1 and PK2): +/- 1 day
- On IPnV1: +/-2 days;
- End of Study / Early Discontinuation: +/- 7 days.

All concentration data-points with deviations outside these permitted ranges will be excluded from the descriptive statistics on concentrations, explained by a footnote in the appropriate tables.

4.3.2 Derivation rules

Concentration below limit of quantification (BLQ) will be imputed according to the rules mentioned in section 2.3.2.

4.3.3 Presentation of results

Efgartigimod concentration actual values will be summarized by means of descriptive statistics at each analysis visit.

Individual concentration data and actual blood sampling times for PK assessments will be listed.

4.4 PHARMACODYNAMICS

4.4.1 Available data

The following pharmacodynamic parameters will be analyzed: total IgG level and autoantibodies (anti-AChR antibodies for the AChR-Ab seropositive participants).

4.4.2 Endpoint and derivation rules

- 1) Actual value and percent change (compared to Baseline and CnB) in total IgG level at each visit.

Analysis will be done by AChR-Ab status and overall.

- 2) Actual value and percent change (compared to Baseline and CnB) in anti-AChR antibodies (in AChR-Ab seropositive participants) at each visit.

See section 2.2.2 for calculation of percent change from baseline.

4.4.3 Statistical analysis

Summary statistics will be provided in terms of absolute values and percent changes from baseline and CnB for each treatment cycle. IgG tables will be done by AChR-Ab status and on the overall safety population, AChR-Ab tables will be done in AChR-Ab seropositive participants only.

	Statistical Analysis Plan	
ARGX-113-2002	Final Analysis	Final 5.0 of 31Jan2025

A sensitivity analysis will be done for the descriptive table on total IgG, excluding the IgG values per cycle after an immunoglobulin related MG therapy or a plasmapheresis procedure during that cycle period.

All data will be listed.

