4.2. Scientific Rationale for Study Design

The aim is to evaluate the long-term safety and tolerability of efgartigimod PH20 SC 1000 mg and its efficacy in patients with gMG. Efgartigimod PH20 SC will include rHuPH20 because the enzyme facilitates the SC delivery of volumes greater than ~2 mL and may increase the absorption and dispersion of efgartigimod. rHuPH20 depolymerizes hyaluronan under physiologic conditions and acts as a permeation enhancer, allowing for a larger volume to be injected with limited swelling or pain.⁴

As per the primary objective (Section 3), long-term safety and tolerability will be assessed by measuring the incidence and severity of TEAEs, including SAEs, AESIs, electrocardiogram (ECG) results, and clinical laboratory assessments over time. These metrics provide a broad view of potential safety concerns and allow a more detailed safety profile for efgartigimod PH20 SC.

An open-label, single-arm design allows for accrual of long-term safety data over multiple TPs to verify the overall safety and tolerability profile of the SC formulation of efgartigimod.

IgG autoantibodies lead to gMG symptoms, resulting from destruction of important molecules in the NMJ, including AChR. Total IgG levels and levels of AChR-Abs will be evaluated in the first year of the study as objective surrogate measures for the treatment efficacy of efgartigimod in gMG. Clinical efficacy will be measured by the MG-ADL total score, which is a well-established measure for assessing disease severity. Furthermore, study ARGX-113-1704 showed that reductions in the MG-ADL total score were consistent with reductions in levels of total IgG and AChR-Abs and followed a similar time course. Any effect on the QoL of the participants will be measured using the MG-QoL15r and EQ-5D-5L assessments, which are standardized assessments for quality of life related to gMG symptoms and generic health status, respectively.

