6.8.2. Permitted Concomitant Medication and Procedures

At study entry, participants are required to be on concomitant therapy for gMG, as they were in the antecedent studies. Permitted concomitant therapy for gMG includes:

- Nonsteroidal immunosuppressant (NSIDs) (eg, azathioprine, methotrexate, cyclosporine, tacrolimus, mycophenolate mofetil, and cyclophosphamide)
- Steroids
- Acetylcholinesterase (AChE) inhibitors

To be retreated at study entry, participants must be on a stable dose of concomitant therapy for gMG. Therefore, participants entering this study from ARGX-113-1705 that have recently adjusted their concomitant medication will have to wait to be retreated in this study for the following time periods after changing their concomitant medication:

- NSIDS: 3 months
- steroids: 1 month
- AChE inhibitors: 2 weeks

In the first year, participants will be allowed to reduce the dose of a corticosteroid, an NSID, or an AChE inhibitor during IPs, but only after the first IP visit following a TP.

During the second year of the study, there will be no restrictions on changes to any concomitant gMG treatment.

All changes in concomitant gMG treatment and the reason for the change must be recorded in the eCRF.

Throughout the entire study, participants may be treated with plasma exchange (PLEX), Ig therapy or immunoabsorption (as a combination or monotherapy) as rescue therapy a maximum of 3 times per year if it is not for a life-threatening condition (see Section 6.8.3).

Participants are allowed to receive vaccines that do not use live or live-attenuated biological material. Any inactivated subunit, polysaccharide, or conjugate vaccine is allowed at the discretion of the investigator and when administered at least 48 hours predose or 48 hours

postdose of the IMP. Any vaccination done during the study should be recorded in the eCRF with the brand name of the vaccine and the date of vaccine administration (see Section 8.2.9).

Standard therapies for concurrent medical conditions are permitted if they are not listed as prohibited in Section 6.8.3.

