6.8.4. Rescue Therapy

PLEX, Ig therapy, immunoabsorption, an increased dose of the current corticosteroid, or the use of a different corticosteroid used as a monotherapy or in combination with another therapy are considered rescue therapy if both of the following conditions apply:

1. The treating physician believes that the participant's health is in jeopardy if rescue therapy is not provided, and
2. The participant is deteriorating clinically according to the protocol-defined criteria, which includes at least 1 of the following:
 - a. new or worsening of respiratory/bulbar symptoms, or
 - b. at least a 2-point increase in any individual nonocular item on the MG-ADL scale compared to the previous visit

The date and time of rescue medication administration, and the name, dosage regimen, and response to the rescue medication will be recorded in the eCRF. Prior to administration of rescue therapy, the MG-ADL total score should be recorded if possible.

Participants who receive rescue therapy under the previously listed conditions will not be discontinued from the study unless rescue therapy is given in response to a life-threatening

situation. Participants may not receive PLEX, Ig therapy, or immunoabsorption more than 3 times per year. When rescue therapy is needed, what therapy was used and the response to that therapy must be documented in the eCRF. The MG-ADL total score will be used to measure the response to the therapy at the safety follow-up (SFU) visit.

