CKD-EPI	Chronic Kidney Disease Epidemiology Collaboration
CnB	cycle n baseline
CRF	case report form
CTCAE	Common Terminology Criteria for Adverse Events
DBP	diastolic blood pressure
DSMB	data safety monitoring board
ECG	Electrocardiogram
eGFR	estimated glomerular filtration rate
EoS	end of study
EQ-5D-5L	EuroQoL 5 Dimensions 5 Levels
EU	European Union
SFU	safety follow-up
gMG	generalized myasthenia gravis
HR	heart rate
ICF	informed consent form
ICH	International Council for Harmonisation
IgG	immunoglobulin G
IMP	investigational medicinal product
IP	intertreatment period
IRR	injection-related reaction

	Statistical Analysis Plan	
ARGX-113-2002	Final Analysis	Final 5.0 of 31Jan2025

ISR	injection site reaction
ITT	intent-to-treat
mITT	modified intent-to-treat
MAA	marketing authorisation application
████████	████████
MedDRA	Medical Dictionary for Regulatory Activities
MG-ADL	myasthenia gravis - activities of daily living
MG-QoL15r	15-item Quality of life scale for Myasthenia Gravis [revised version]
Nab	neutralizing antibody
NAP	not applicable
OLE	open-label extension
PK	pharmacokinetic(s)
PD	pharmacodynamic(s)
PYFU	patient years of follow-up
QTc	corrected QT interval
QTcB	Bazett's corrected QT interval
QTcF	Fridericia's corrected QT interval
RO	Rollover
SAP	statistical analysis plan
SAF	safety analysis set
SBP	systolic blood pressure
SD	standard deviation
SE	standard error
SGS CR	SGS Clinical Research
SOP	standard operating procedure
STAT	Statistics
TEAE	treatment-emergent adverse event
████████	████████
VS	vital signs
WHO	World Health Organisation
WI	work instruction

SGS	Statistical Analysis Plan	
ARGX-113-2002	Final Analysis	Final 5.0 of 31Jan2025

DEFINITION OF TERMS

AChR-Ab seronegative participants	AChR-Ab seronegative participants refers to participants in whom the anti-AChR-Ab could not be detected at screening in 1705/2001
case report form (CRF)	A printed, optical, or electronic document designed to record protocol required information to be reported to the sponsor for each trial subject.
Cohort	In the context of analysis by cohorts, cohort n is defined as all participants in at least n efgartigimod PH20 SC cycles
Display	Analysis table, figure or listing
MG therapy	Any therapy falling in one of the following categories per appendix 9.3: steroids, NSIDs or AChE inhibitors
Phase	Interval of time in the planned conduct of a study associated with a specific purpose: for example, screening, treatment, follow-up.

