1.1 STUDY OBJECTIVES

According to the protocol, the objectives and endpoints of this study are:

Objectives	Endpoints
Primary	
To evaluate the long-term safety and tolerability of efgartigimod PH20 SC in participants with gMG	Incidence and severity of adverse events (AEs), incidence of serious adverse events (SAEs) and AEs of special interest (AESIs) and changes in laboratory test results, physical examination results, vital signs, and electrocardiogram results
Secondary	
To evaluate the impact of efgartigimod PH20 SC on disease severity	Myasthenia Gravis Activities of Daily Living (MG-ADL) total score changes from baseline and cycle baseline over time by cycle
To evaluate the effect of efgartigimod PH20 SC on pharmacodynamics (PD)	Percentage reduction in levels of total immunoglobulin G (IgG) from baseline and cycle baseline over time by cycle Percentage reduction of acetylcholine receptor binding autoantibodies (AChR-Ab) from baseline and cycle baseline over time by cycle in AChR-Ab seropositive participants
To evaluate the PK of efgartigimod PH20 SC	Efgartigimod serum concentrations
To evaluate the immunogenicity of efgartigimod PH20 SC	Incidence and prevalence of anti-drug antibodies (ADAs) to efgartigimod over time Incidence and prevalence of neutralizing antibodies (NAb) against efgartigimod over time Incidence and prevalence of ADAs to rHuPH20 over time Incidence and prevalence of NAb against rHuPH20 over time
To evaluate the impact of efgartigimod PH20 SC on the quality of life (QoL) of the participants	Changes in total Myasthenia Gravis Quality of Life Questionnaire (15-item scale revised) (MG-QoL)

[figure not shown]
SGS	Statistical Analysis Plan	
ARGX-113-2002	Final Analysis	Final 5.0 of 31Jan2025

	
QoL15r) from baseline and cycle baseline by cycle
 
Changes in EuroQoL 5 Dimensions 5-Level (EQ-5D-5L) visual analog scale (VAS) score from baseline and cycle baseline over time by cycle
 
EQ-5D-5L responses to 5 dimensions (ie, mobility, self-care, usual activities, pain/discomfort, anxiety/depression) over time by cycle

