9.3 MG THERAPIES AND PROCEDURES

Steroids	NSIDs	AChE inhibitors	Other	Procedures
PREDNISONE	CICLOSPORIN	NEOSTIGMINE	ECULIZUMAB	PLASMAPHERESIS
PREDNISOLONE	AZATHIOPRINE	NEOSTIGMINE BROMIDE	NIPOCALIMAB	THYMECTOMY
METHYL PREDNISOLONE	MYCOPHENOLATE MOFETIL	PYRIDOSTIGMINE	RITUXIMAB	ELECTRONEUROGRAPHY
HYDROCORTISONE	MYCOPHENOLATE SODIUM	PYRIDOSTIGMINE BROMIDE	IMMUNOGLOBULINS	FEEDING TUBE USER
TRIAMCINOLONE	MYCOPHENOLIC ACID	AMBENONIUM	IMMUNOGLOBULINS NOS	GASTROSTOMY ^a
DEFLAZACORT	METHOTREXATE	AMBENONIUM CHLORIDE	IMMUNOGLOBULIN THERAPY	ELECTROMYOGRAM
METHYL PREDNISOLONE SODIUM SUCCINATE	TACROLIMUS	DISTIGMINE	IMMUNOGLOBULIN HUMAN NORMAL	ENTERAL NUTRITION
PREDNISOLONE ACETATE	CYCLOPHOSPHAMIDE	DISTIGMINE BROMIDE	IMMUNOGLOBULIN G HUMAN	IMMUNOADSORPTION THERAPY
	CYTOPHOSPHANE			
	TACROLIMUS MONOHYDRATE			

^a Study physician will review case by case for this procedure to decide whether MG-related or not.

Statistical Analysis Plan

ARGX-113-2002

Final Analysis

Final 5.0 of 31Jan2025

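### The total IgG sensitivity analysis keeps values taken after immunoadsorption, a permitted rescue, because its exclusion rule names only immunoglobulin therapy and plasmapheresis

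*SAP*

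**What the plan says.** The endpoint is secondary and pharmacodynamic. SAP section 1.1 gives it as "Percentage reduction in levels of total immunoglobulin G (IgG) from baseline and cycle baseline over time by cycle". Protocol section 4.2 limits the data in time: "Total IgG levels and levels of AChR-Abs will be evaluated in the first year of the study".

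For total IgG, SAP section 4.4.3 adds a sensitivity version of the descriptive table, "excluding the IgG values per cycle after an immunoglobulin related MG therapy or a plasmapheresis procedure during that cycle period". The table list carries it as Table 14.2.5.1.2 and, by AChR-Ab status, Table 14.2.5.1.4. It also lists an AChR-Ab sensitivity table, 14.2.5.2.2, for which section 4.4.3 gives no rule.

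Protocol section 6.8.2 says that "participants may be treated with plasma exchange (PLEX), Ig therapy or immunoabsorption (as a combination or monotherapy) as rescue therapy". Section 6.8.4 opens its definition of rescue with the same three: "PLEX, Ig therapy, immunoabsorption, an increased dose of the current corticosteroid". A rescued participant "will not be discontinued from the study unless rescue therapy is given in response to a life-threatening" situation; section 7.2 adds discontinuation for rescue more than 3 times per year.

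SAP appendix 9.3 lists "IMMUNOADSORPTION THERAPY" in its Procedures column as an entry separate from plasmapheresis. The immunoglobulin terms are in the column headed Other. The SAP's definition of terms describes MG therapy as "Any therapy falling in one of the following categories per appendix 9.3: steroids, NSIDs or AChE inhibitors".

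**The concern.** The rule sets aside IgG values that follow a non-study intervention acting on immunoglobulins. The protocol names three such rescues in one breath, and the rule picks up two. A programmer working from the text would keep values after immunoadsorption, although the SAP already has a code that identifies them. If the procedure removes IgG, a value taken after it and compared with a baseline taken before it shows a reduction that is partly not due to efgartigimod. The table meant to set such values aside would still contain some of them.

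The trigger wording is also loose. Under the SAP's own definition of MG therapy, immunoglobulins are not an MG therapy, so even the first trigger has to be interpreted.

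**Working it through.** The plan states no figure to reproduce: the study is descriptive, with no hypothesis and no sample size calculation (Protocol sections 9.1 and 9.2). The check is a comparison of texts, followed by an illustration of size.

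**Step 1. Triggers against permitted rescues.**

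| Rescue (Protocol 6.8.2, 6.8.4) | Code in SAP appendix 9.3 | Trigger in SAP 4.4.3? |
|---|---|---|
| Ig therapy | Immunoglobulin terms, column Other | Yes, by intent; the MG therapy definition does not include that column |
| Plasma exchange (PLEX) | Plasmapheresis, column Procedures | Yes, taking the two terms as equivalent |
| Immunoabsorption (protocol spelling), taken as immunoadsorption | Immunoadsorption therapy, column Procedures | No |

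Two of the three are covered. Neither the table titles, which add only the label of a sensitivity analysis, nor any other SAP section extends the rule.

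**Step 2. Can affected values exist?** Yes. Rescued participants normally stay in the study. The year 1 schedule (Protocol Table 1) marks PD sampling at the first visit of each treatment period, at the intertreatment visits, at ET/SFU and at unscheduled visits. A sample after rescue within the same cycle is therefore possible. Whether any exists, the documents do not say.

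**Step 3. Direction within a cycle.** SAP section 2.2.2 gives percent change as 100 × (value − baseline) / baseline. With a baseline taken before the procedure, a later value lowered by the procedure makes the change more negative, so the reduction looks larger. This holds only for values after the procedure compared with a baseline before it.

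**Step 4. Size, by assumption only.** Let f be the share of values in a table cell that follow immunoadsorption, d the extra percentage-point reduction in those values, and m the mean reduction otherwise, taken as the same for affected and unaffected values. The cell mean is then (1 − f) × m + f × (m + d) = m + f × d, so the shift is f × d. The documents give neither f nor d.

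- Low: f = 1%, d = 10 points: 0.01 × 10 = 0.1 point.
- High: f = 5%, d = 40 points: 0.05 × 40 = 2.0 points.
- Small late-cycle cell: 1 of 10 values, d = 40 points: 0.10 × 40 = 4 points.

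For scale, Protocol section 10.6.1 cites a maximum mean total IgG reduction of 60% to 70% in previous studies. Small cells are plausible: results are split by cycle, treatment group and AChR-Ab status, descriptive outputs are repeated for Japanese and non-Japanese participants, and full descriptive statistics are shown from 2 observations upward (SAP sections 2.4 to 2.4.2 and 4.4.3).

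**The case against.** The strongest reply is that little depends on this. It is a descriptive sensitivity table for a secondary endpoint, with PD measured in year 1 only. The main table keeps all values in any case. Total IgG, concomitant procedures and rescue therapies are all listed, so an affected value can be traced by hand. No document shows that any participant received immunoadsorption, and none states that it lowers IgG. All of this stands, and it caps the importance of the point. It does not supply the missing trigger.

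Three stronger readings are tempting, and the documents do not support them.

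- A reader might infer that, because the exclusion ends with the cycle, the next cycle baseline is contaminated in the same direction and should be excluded. For a given later value, a lower cycle baseline makes the percent reduction from that baseline smaller, the opposite direction to Step 3. SAP section 2.2.4 also assigns the last assessment before a new cycle to the old cycle as well as to the new baseline, so the existing rule can be read as partly covering it. Protocol section 6.5.1 requires at least 28 days between any rescue and retreatment, which limits carry-over, although the documents do not show that this is long enough. Excluding a cycle baseline would cost all of that participant's changes from that baseline in the cycle.
- A reader might expect values after immunoadsorption and values after Ig therapy to offset each other to an unknown degree. Within a cycle, the rule already drops the values after Ig therapy, so none are left in that cycle to offset.
- A reader might take the table as declared by the SAP to be free of all non-study procedures. The SAP states no such purpose; it states only the rule.

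**Conclusion.** The omission is real as the rule is written: values after immunoadsorption in the same cycle stay in the total IgG sensitivity analysis, while those after the two companion rescues are removed. If immunoadsorption lowers IgG, the retained values overstate that cycle's reduction. That premise is an assumption from the nature of the procedure and its grouping with plasma exchange.

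The size is unknown and may be nil. The 0.1 to 2.0 point range, and the 4 points in a cell of 10, are illustrations with assumed inputs, not estimates. No claim is made about an overall direction of bias across cycles. This is a low-priority wording repair, worth making because it is nearly free.

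**What to change.** In SAP section 4.4.3, replace the descriptive triggers with the appendix 9.3 terms: all immunoglobulin terms, plasmapheresis and immunoadsorption therapy. This adds the missing procedure and removes the dependence on the MG therapy definition. State that the list applies to Tables 14.2.5.1.2 and 14.2.5.1.4, and also to the AChR-Ab sensitivity Table 14.2.5.2.2. No mandatory exclusion of the next cycle baseline is needed.

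The cost is a few words and one added code in the selection of records. The terms are already in the appendix, and no new data are collected. At most, the few values that follow immunoadsorption leave the sensitivity tables; the main tables do not change. Record the change in SAP section 6, under 6.1 or 6.2 according to whether the database has been locked.
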